13.1 Recruitment rates

A feasibility questionnaire was sent out to the six lead study sites. The following numbers of patients fulfilling inclusion criteria per year were reported: Liverpool: 1800, Leeds: 2000, other sites 1000 each, Total: ~11000/year. If only 50- 70% of eligible patients provide deferred consent following randomisation, then the sample size of 7676 is easily achievable over 24 months.

Once all processes of screening and data collection are embedded at each site, we anticipate between 40 - 70 participants per month. In our projections, we have also taken seasonality into account, as the rate of infections is likely to be higher in the winter months.

14 Qualitative data collection and analysis

The qualitative work will have three components: interviews with clinicians, interviews with patients/carers, and observations of trial implementation. Findings will be used to aid understanding of the quantitative data and provide areas for improvement in processes to enhance the efficiency of the trial.

Interviews with ED clinicians

These will take place at two time points. Interview 1 will take place during the pilot phase and will be a semi-structured interview with 10-12 clinicians at <5 study sites (2-3 per site). This will explore the feasibility and acceptability of research processes and integration of the PCT algorithm into their ED setting. Interview 2 will be with clinicians towards the end of the trial when they have more experience of using the PCT algorithm and will identify barriers and facilitators to the use of the PCT test and algorithm in more detail, including reasons for varying from study guidelines.

Interviews with patients

We will conduct semi-structured interviews with patients after the 90 days follow-up point has been reached, in order to gain a detailed understanding of patients' experiences of care

to aid understanding of trial results. We will encourage patients to include a close family member or friend, where possible, in the interview also. This will allow us to capture an additional perspective on the patient's care. Our proposed sample size is 25-30 patients. This was found to be a sufficient sample size in previous qualitative research (BATCH Trial) exploring clinicians' and patients' perspectives on antibiotic resistance and infection management. If a patient lacks capacity at the time of consent for the main trial, consultees will be given an option to consent to being approached by qualitative researchers to take part in an interview. Witnessed consent may be obtained over the telephone or web video link if hospital visiting rules or parental infection mean a parent/guardian cannot be physically present.

Observations

Ethnographic observation of trial processes will be carried out in ≤ 5 participating sites. We propose a period of observation of 1-3 days based on our previous research (BATCH trial). The observations and field notes of trained qualitative researchers will enable us to understand how the individual intervention components and delivery processes work across different local EDs, and the complex environment in which consent is taken. This will allow us to explore adherence, feasibility, implementation, and practicality of intervention. We will observe how HCPs 'use' their clinical judgement to interpret the PCT and NEWS2 assessment to make decisions within a busy ED, and with pressure to initiate intravenous antibiotics for high risk patients within one hour. Including: what is 'treatment as usual', whether there is learned behaviour from professionals as they alter their 'treatment as usual' behaviour in the light of the information they gain on specific patient groups, and what influence the introduction of protocolised behaviour has on clinical behaviour and decision making regardless of the PCT test result. We will also explore reasons for compliance or non-compliance with the algorithm. We will engage key HCPs from the trial to co-produce site-specific data collection plans for observations. This will help us to plan what the observation of trial implementation will include; which aspects of the trial will be of most and least interest to observe and why; whether there are scheduled activities / meetings where an observer would be welcome; what are the different HCP roles within the study and who would be good to observe.

14.1 Qualitative interview sampling methods

We will be pragmatic in sample size and the need to conduct further interviews will be based on preliminary analysis/interviewer field notes indicating whether the data collected sufficiently answers the research questions [33]. We will review whether there is sufficient breadth and depth of data, whether interview participants are representative of the study population, and practical aspects of recruitment (attempts to invite participants, numbers declined, and withdrawn). We will continually review our sampling decisions and we will keep detailed notes on our sampling strategy to maintain transparency [33].

We will purposefully sample participants for interview. To create our sampling framework, we will identify specific interviewee characteristics with input from the TMG (including patient representative and consultants) and information from our rapid literature review. We will use the PRONTO trial patient database to select interviewees with maximum variation in our specified characteristics. We propose that the characteristics for each group are:

Patients:

- Treatment arm (include patients who received standard care and PCT guided care)
- High, low or medium risk of sepsis at time of presentation (to vary severity of case and the degree of anxiety patients may have experienced)
- Antibiotic therapy (to capture experiences of a range of different treatment outcomes)
- Hospital site (to explore local contextual factors influencing patient experiences of care)

Health Professionals:

- Role: e.g. consultant, research nurse, staff nurse, patient flow matron etc. (to gain a wide perspective on how patient cases are assessed and treatment decisions are made and the impact on patient flow through the ED).
- Hospital site (to explore local contextual factors that act as facilitators or barriers to the test in the intervention arm, and whether there are regional differences in standard care).

We will remain flexible in our sampling framework, as once the study begins we may find some characteristics are more or less important than others or identify additional characteristics. Data collection will be iterative, allowing preliminary analysis to guide the subsequent sampling decision and selection of further interviewees.

14.2 Qualitative Analysis

Interview transcripts and field notes of observations will be analysed using a framework approach [34] to take into account the different interviewee characteristics e.g. different sites, different arms of the trial etc. We will develop a thematic framework based on the research objectives and emerging themes. Transcripts will be double-coded until consensus is reached. The thematic framework will be applied to data using the qualitative software package, NVivo 11.

15 Safety reporting

The Principal Investigator is responsible for ensuring that all site staff involved in this trial are familiar with the content of this section.

All SAEs must be reported immediately (and within 24 hours of knowledge of the event) by the PI at the participating site to the CTR Trial team unless the SAE is specified as not requiring immediate reporting (see section 13.2).

For the purposes of this trial, SAEs will need reporting if the event:

- Results in persistent or significant disability or incapacity
- Consists of a congenital anomaly or birth defect

The trial population comprises very sick adults, and hospitalisation is normal in this population. Events such as prolongation of existing hospitalisation, life threatening events and death are also expected in this population and are recorded as part of routine data collection and therefore are not subject to expedited reporting on an SAE form.

15.1 Definitions

Term	Definition
Adverse Event (AE)	Any untoward medical occurrence in a participant or clinical trial participant administered a medicinal product and which are not necessarily caused by or related to that product
Serious Adverse Event (SAE)	Any adverse event that - 
 • Results in persistent or significant disability or incapacity • Consists of a congenital anomaly or birth defect

15.2 Trial Specific SAE Reporting requirements

[figure not shown]
As stated above death is a primary outcome of the trial and is recorded as part of routine data collection, therefore are not subject to expedited reporting on an SAE form.

For the purposes of this trial the following events will **not** require reporting as SAEs:

- Death
- Life threatening event
- Hospitalisation or prolongation of hospitalisation
- Admission to Intensive Care Unit (ICU)
- Non serious AEs potentially attributable to PCT test and step down approach will be collected as part of routine follow up at 28 days.
- Other non-serious AEs will not be collected.

These events should be recorded in the participant's notes and on the relevant CRF and forwarded to the CTR in the normal timeframes for CRF completion. A flowchart (Figure 4) is given below to illustrate reporting procedures.

Figure 4: SAE reporting procedures flow diagram

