5.4 Secondary outcomes measure(s)

Time until initiation of IV antibiotic therapy

Late IV antibiotic initiation – antibiotics commenced after 3 hours

Number of days on IV antibiotics (during admission and total over the first 28 days).

Number of days on any antibiotic (during admission and total over the first 28 days).

Number of days on broad spectrum antibiotics (IV and oral), defined by number of days on an Access group of antibiotics as defined by WHO [AWaRe Classification Database](#) (during admission and total over the first 28 days).

ICU admission – at any point during admission

Length of ICU stay

Length of hospital stay

Adverse antibiotic outcomes

Readmission to hospital within 90 days

Mortality within 90 days (and time until death)

Health utility (EQ-5D/5L) at 28 and 90 days

Health resource usage

Feasibility of implementing PCT testing alongside NEWS2 scoring in EDs

Acceptability of implementing PCT testing alongside NEWS2 scoring in EDs, to patients, carers and clinicians

Planned stratification of all outcomes by COVID-19 diagnosis

6 Trial design and setting

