This will be used in combination with NEWS2 assessment of adult patients with suspected sepsis in ED, using a guidance-only algorithm for clinicians (see flow chart). It is important to note that clinicians have oversight at all times as to whether to adhere to the algorithm. As currently mandated in NICE clinical guidelines and quality standard QS161, urgent senior review within an hour will take place where any health care provider identifies at least one risk factor indicating high risk of severe illness or death regardless of aetiology. In the intervention arm a NEWS2 score of 5 or 6, combined with a PCT score of <0.5 indicates a low risk of bacterial sepsis, but an urgent senior review is mandated on the basis of the elevated NEWS2 score in keeping with standard QS161. For participants who are identified as medium risk, urgent senior review will occur. Antibiotics will be delivered according to clinical assessment. For participants in the high risk categories (Figure 1, red boxes), antibiotics will be given within the hour along with blood tests and IV fluids given as per standard care.

The PCT result is a decision aid and not to be used as a definitive management decision tool. Trained HCPs will perform the test in the ED, without the need to send the PCT sample to the laboratory. A rapid result, especially if it indicates a low or medium risk, may provide reassurance to patients and families, and reduce anxiety.

[figure not shown]
Full administrator level training will be provided by Thermofisher or AB Scientific at each site with all users following the appropriate Standard Operating Procedure for QC measurement and routine work flow processes (see example of BRAHMS PCT Direct in Figure 3). For the BRAHMS PCT Direct, Research Nurses or appropriately delegated HCPs will have a unique 4-

digit log in code for the reader. Adults in the control arm will not have the PCT test performed and will simply have NEWS2 assessment for suspected sepsis as per standard care.

Thermo Scientific B·R·A·H·M·S direct Reader

Routine workflow

1/3

thermo scientific

Figure 3. Routine work flow for BRAHMS PCT-Direct Reader.

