11.1 Assessments

Outcome data will be recorded daily by the research nurse for all recruited participants (up to and including Day 28, or until discharge). Patient reported outcome data (health-related quality of life and resource use questionnaires) will be recorded at day 28 and day 90 (with the exception of those recruited within the last 3 months of the study).

Research nurses will review observation and medication charts, and medical notes for all recruited participants to collect the data described in Table 1 below:

Table 1: Outcome data collection

Outcome	Data Source	Type of data	Frequency	By Whom
Antibiotic (Abx) initiation	Observation (Obs) charts/medical notes/drug charts	Time of initiation, Abx type, dose, duration	Admission/Daily	Research Nurse
Abx use (IV and Oral) in-patient	Obs charts/medical notes/drug charts	Abx type, dose, duration	Daily	Research Nurse
Abx use (IV and Oral) post discharge up to 28 days	Obs charts/medical notes/drug charts/patient report/GP record	Abx type, dose, duration	At 28 day	Research Nurse
Adverse events	Obs charts/medical notes	Date, type	Daily	Research Nurse
ICU usage	Medical notes	Date, details of admission to ICU	Daily	Research Nurse
COVID diagnosis	Medical notes	Date, clinical or laboratory confirmed	At 28 day	Research Nurse
Unscheduled readmissions	Medical notes	ICU re-admissions, re-admissions post discharge	Daily	Research Nurse
Mortality	Medical notes	Date, Description	If before Day 28	Research Nurse
Discharge	Medical notes	Date, Description	If before Day 28	Research Nurse
Serious Adverse Drug Reactions (ADRs)	Medical notes	ADR(s)	Daily	Research Nurse
Health utility	Patient reported	-	Day 28 and Day 90	EQ-5D/5L, Patient reported questionnaire, collected by

				telephone or by post
Health-related Quality of Life (EQ-5D/5L)	Patient reported	-	Day 28 and Day 90	Patient reported, collected by telephone, or by post
Resource use	Patient reported	Direct medical costs and resource use	Day 28 and Day 90	Patient reported, collected by telephone, or by post

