15.5 Reporting procedures

15.5.1 Participating Site Responsibilities

The PI (or delegated appropriately qualified doctor from the trial team) should sign and date the SAE CRF to acknowledge that he/she has performed the seriousness and causality assessments. Investigators should also report SAEs to their own health boards or trust in accordance with local practice.

A completed SAE form for all events requiring immediate reporting should be sent via email to the CTR within 24 hours of knowledge of the event. A separate form must be used to report each event, irrespective of whether or not the events had the same date of onset.

The participant will be identified only by trial number, date of birth and initials. The participant's name should not be used on any correspondence.

It is also required that sites respond to and clarify any queries raised on any reported SAEs and report any additional information as and when it becomes available through to the resolution of the event. Additionally, the CTR may request additional information relating to any SAEs and the site should provide as much information as is available to them in order to resolve these queries.

Serious Adverse Event (SAE) email address:

[contact]

Serious adverse events should be reported from randomisation, throughout the treatment period up to, and including 28 days after the participant is randomised.

An SAE form is not considered as complete unless the following details are provided:

- Full participant trial number
- An Adverse Event
- A completed assessment of the seriousness, and causality as performed by the PI (or another appropriately medically qualified doctor registered on the delegation log).

If any of these details are missing, the site will be contacted and the information must be provided by the site to the CTR within 24 hours.

All other AEs should be reported on the CRF following the CRF procedure described in Section 16.

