Antibiotic usage	No of days on IV antibiotics No of days on all antibiotics No of days on broad spectrum antibiotics	In hospital	Linear regression
Antibiotic adverse outcomes	Anticipated drug reactions include: diarrhoea, C. difficile , acute kidney injury, hearing loss etc.	In hospital	Logistic regression
ICU usage	People admitted to ICU No of days in ICU	In hospital	Logistic regression Linear regression
Readmission to hospital	People with one or more readmissions	After discharge	Logistic regression
Mortality	Time until death	90* days	Cox regression
Health utility	EQ-5D-5L	90* days	Linear regression of transformed outcome measure

* Except for patients recruited during the last 3 months of the study.
Full details of all analyses will be provided in the PRONTO SAP.

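### Section 15.2 says most non-serious AEs will not be collected; this contradicts Table 1 and 15.5.1 and puts the secondary outcome on antibiotic adverse events at risk of incomplete or uneven recording

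*Protocol*

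**What the plan says.** **The outcome.** Section 5.4 lists "Adverse antibiotic outcomes" among the secondary outcomes, and the synopsis has an equivalent entry. Table 3 in section 17.1 describes the measure ("Anticipated drug reactions include: diarrhoea", followed by *C. difficile*, acute kidney injury and hearing loss as further examples). It sets the time frame as in hospital and the analysis as logistic regression.

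**The narrow rule.** Section 15.2 lists events that need no SAE report. Its last two bullets go further and deal with collection: "Non serious AEs potentially attributable to PCT test and step down approach will be collected as part of routine follow up at 28 days", then "Other non-serious AEs will not be collected".

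**The wider rules.**
- Section 11 names adverse events among the assessments for all participants.
- Table 1 in section 11.1 has a row reading "Adverse events Obs charts/medical notes Date, type Daily Research Nurse". The lead-in applies the table to all recruited participants.
- Section 15.5.1 says "All other AEs should be reported on the CRF following the CRF procedure described in Section 16".
- The sentence that closes the 15.2 list says "These events should be recorded in the participant's notes and on the relevant CRF".

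**Seriousness and arms.** Section 15.1 counts an event as serious only if it results in persistent or significant disability or incapacity, or is a congenital anomaly or birth defect. Section 10 says "Adults in the control arm will not have the PCT test performed".

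**The concern.** The outcome can be analysed only if antibiotic reactions are recorded in the same way for everyone. Section 15.2, taken at its word, excludes a non-serious reaction unless someone links it to the PCT test and step-down approach. Most of the Table 3 events would be non-serious under 15.1, so the exclusion covers most of the outcome. The permitted exception turns on a test that control patients do not have, and staff making the attribution know the allocation.

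The background section gives antibiotic-related adverse reactions as one of the harms of over-prescribing, so this outcome speaks to an expected benefit of the intervention. Events never entered on the CRF cannot be recovered at the analysis stage, whatever the statistical analysis plan says.

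**Working it through.** No stated figure depends on this point, so the check sets the rules side by side and follows one event through them.

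**1. The rules compared**

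| Place | Non-serious AEs covered | Attribution needed | Timing |
|---|---|---|---|
| 15.2, last two bullets | Only those linked to the PCT test and step-down approach | Yes | Follow-up at 28 days |
| 15.2, closing sentence | The listed events | No | Normal CRF timing |
| Table 1, AE row | No limit stated | No | Daily |
| 15.5.1 | All other AEs | No | Refers to Section 16 |
| Table 3 (analysis) | Antibiotic reactions | None stated | In hospital |

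The closing sentence of 15.2 cannot be reconciled with the bullet just above it: it sends to the CRF a list that includes events said not to be collected.

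**2. One event followed through.** Take antibiotic-related diarrhoea in hospital that leaves no lasting disability.
- Under 15.1 it is not serious, so no SAE form is completed.
- The antibiotic-specific item in section 11 and Table 1 is for serious adverse drug reactions. If serious has its 15.1 meaning there, this item does not capture the event.
- Under 15.2 it is collected only if linked to the PCT test and step-down approach.
- Under the Table 1 AE row and 15.5.1 it is recorded.

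Non-serious antibiotic reactions therefore depend on the general AE instructions, which are the ones 15.2 contradicts. The same holds for acute kidney injury that merely prolongs the stay, because prolonged hospitalisation is outside the 15.1 definition.

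**3. Which rule prevails.** Nothing says. Section 15 opens by making the Principal Investigator responsible for staff knowing its content, so 15.2 is a rule that sites may reasonably follow.

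**4. What could happen**
- All sites follow Table 1: no loss and no bias.
- Sites follow 15.2 and attribute reactions to the antibiotic: non-serious events are lost in both arms.
- Sites follow 15.2 and some intervention-arm reactions are linked to the test or the step-down approach: recording differs by arm.

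**5. Can the effect be sized?** Let p be the true rate, equal in both arms, and r1 and r0 the fractions recorded in the intervention and control arms. The apparent odds ratio is [p·r1/(1 − p·r1)] / [p·r0/(1 − p·r0)]. The protocol gives none of these inputs. Assuming p = 10% purely for illustration, with complete recording in the other arm:

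| Events lost | Lost in control only | Lost in intervention only | Lost equally |
|---|---|---|---|
| 10% | (0.10/0.90)/(0.09/0.91) = 1.12 | 1/1.12 = 0.89 | 1.00 |
| 25% | (0.10/0.90)/(0.075/0.925) = 1.37 | 1/1.37 = 0.73 | 1.00 |
| 50% | (0.10/0.90)/(0.05/0.95) = 2.11 | 1/2.11 = 0.47 | 1.00 |

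The result lies on either side of 1, or at 1, depending only on the assumption. The table shows that the comparison is sensitive to uneven recording. It does not estimate what happens in this trial.

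**6. Cross-reference.** Section 15.5.1 points to Section 16 for the CRF procedure. Section 16 is Statistical considerations; CRF completion is in section 19.1.

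**The case against.** The strongest reply is that 15.2 is a safety-reporting section. Its heading and the lead-in to its list concern SAE reporting, and its closing sentence sends the listed events to the CRF. Outcome collection is set in section 11.1, where research nurses review charts and notes daily for all recruited participants, with an AE row not limited by arm, seriousness or attribution. Serious antibiotic reactions also have their own row, in both arms.

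Much of this stands. A reader might infer from 15.2 that the outcome is collected unequally between arms or hardly at all. The documents do not support that, because several other places direct wider collection and no single rule leaves the outcome uncollected. A reader might also infer a bias against the PCT arm. That is not established either: a reaction would more naturally be attributed to the antibiotic than to a blood test, and under 15.2 it would then be missed in both arms.

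The reply does not remove the contradiction. The two bullets speak of collecting events, not of reporting them as SAEs. If only expedited reporting was meant, the wording says something else. The serious-reaction row does not reach most of what Table 3 lists.

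The available text does not define the step-down approach. The flow diagrams are not reproduced in the copy reviewed, so no weight is placed on that.

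**Conclusion.** The protocol contradicts itself on whether non-serious AEs unrelated to the PCT test are collected, and the narrow version conflicts with a named secondary outcome. The consequence is a risk of incomplete recording, possibly differing by site and by arm. Its size and direction cannot be derived from the documents, and there is no effect if every site works from Table 1.

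The conclusion assumes that serious in the drug-reaction row carries its 15.1 meaning and that some sites would apply 15.2 as worded. It does not touch the co-primary outcomes. It should be corrected, because the defect is in data capture and the remedy is cheap.

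**What to change.** 1. In 15.2, limit the exclusion to SAE and expedited reporting, and delete the sentence saying that other non-serious AEs are not collected.
2. State that the antibiotic adverse outcomes in Table 3, serious or not, are recorded as outcome data for every participant in both arms, from the same sources and on the same CRF items, without an attribution filter, over the Table 3 window (in hospital).
3. Align Table 1 and 15.5.1 with this, including the timing (28-day follow-up in 15.2, daily in Table 1, in hospital in Table 3). Point the 15.5.1 cross-reference to section 19.1.

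The window should stay as Table 3 has it. Extending it to day 28 would change the outcome and require collection after discharge, which the daily chart review does not cover.

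The cost is a protocol wording change and slightly more CRF recording, within the review of charts and notes already planned for all participants. The CRF itself is not among the documents, so whether its items need changing has to be checked.
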